#### **7.3.2.2 Visit 6**

#### **Visit 6 (>100 days and <150 days post-transplant):**

#### **CONFIDENTIAL**

This material is the property of the NYU School of Medicine and Langone Medical Center. Do not disclose or use except as authorized in writing by the study sponsor

- The subject will be seen in follow-up between 100-150 days post-transplant for assessment of adverse events, with specific attention to non-infectious pneumonia syndrome. All interval thoracic imaging performed will be reviewed along with the interval history.

### 7.3.3 Final Study Visit

- Subjects will be seen one year after transplant ( $\pm$  4 weeks) for assessment of relapse free survival. Progression or relapse will be determined by reviewing the medical history and/or consulting with the transplant team if applicable. All interval thoracic imaging performed will be reviewed along with the interval history.
- Pulmonary function test assessments

### 7.3.4 Withdrawal/Early Termination Visit

If a subject withdraws after total body irradiation but before their final study visit, their withdrawal will be documented. Adverse event data will be recorded at this visit regardless of the interval from transplant. All interval thoracic imaging performed will be reviewed along with the interval history.

## 7.4 Concomitant Medications, Treatments, and Procedures

All concomitant prescription medications taken during study participation will be recorded on the case report forms (CRFs). For this protocol, a prescription medication is defined as a medication that can be prescribed only by a properly authorized/licensed clinician. Medications to be reported in the CRF are concomitant prescription medications, over-the-counter medications and non-prescription medications.

## 8 Assessment of Safety

### 8.1 Specification of Safety Parameters

#### 8.1.1 Definition of Adverse Events (AE)

An **adverse event** (AE) is any symptom, sign, illness or experience that develops or worsens in severity during the course of the study. Intercurrent illnesses or injuries should be regarded as adverse events. Abnormal results of diagnostic procedures are considered to be adverse events if the abnormality:

- results in study withdrawal
- is associated with a serious adverse event
- is associated with clinical signs or symptoms
- leads to additional treatment or to further diagnostic tests
- is considered by the investigator to be of clinical significance

#### 8.1.2 Definition of Serious Adverse Events (SAE)

##### Serious Adverse Event

Adverse events are classified as serious or non-serious. A **serious adverse event** is any AE that is:

- fatal
- life-threatening
- requires or prolongs hospital stay
- results in persistent or significant disability or incapacity
- a congenital anomaly or birth defect

CONFIDENTIAL

This material is the property of the NYU School of Medicine and Langone Medical Center. Do not disclose or use except as authorized in writing by the study sponsor

- an important medical event

Important medical events are those that may not be immediately life threatening, but are clearly of major clinical significance. They may jeopardize the subject, and may require intervention to prevent one of the other serious outcomes noted above. For example, drug overdose or abuse, a seizure that did not result in in-patient hospitalization, or intensive treatment of bronchospasm in an emergency department would typically be considered serious.

All adverse events that do not meet any of the criteria for serious should be regarded as ***non-serious adverse events***.

### 8.1.3 Definition of Unanticipated Problems (UP)

#### Unanticipated Problems Involving Risk to Subjects or Others

Any incident, experience, or outcome that meets all of the following criteria:

- Unexpected in nature, severity, or frequency (i.e. not described in study-related documents such as the IRB-approved protocol or consent form, the investigators brochure, etc)
- Related or possibly related to participation in the research (i.e. possibly related means there is a reasonable possibility that the incident experience, or outcome may have been caused by the procedures involved in the research)
- Suggests that the research places subjects or others at greater risk of harm (including physical, psychological, economic, or social harm).

## 8.2 Classification of an Adverse Event

### 8.2.1 Severity of Event

For AEs not included in the protocol defined grading system, the following guidelines will be used to describe severity.

- **Mild** – Events require minimal or no treatment and do not interfere with the participant's daily activities.
- **Moderate** – Events result in a low level of inconvenience or concern with the therapeutic measures. Moderate events may cause some interference with functioning.
- **Severe** – Events interrupt a participant's usual daily activity and may require systemic drug therapy or other treatment. Severe events are usually potentially life-threatening or incapacitating.

### 8.2.2 Relationship to Study Agent

For all collected AEs, the clinician who examines and evaluates the participant will determine the AE's causality based on temporal relationship and his/her clinical judgment. The degree of certainty about causality will be graded using the categories below.

- **Definitely Related** – There is clear evidence to suggest a causal relationship, and other possible contributing factors can be ruled out. The clinical event, including an abnormal laboratory test result, occurs in a plausible time relationship to drug administration and cannot be explained by concurrent disease or other drugs or chemicals. The response to withdrawal of the drug (dechallenge) should be clinically plausible. The event must be pharmacologically or phenomenologically definitive, with use of a satisfactory rechallenge procedure if necessary.

#### CONFIDENTIAL

This material is the property of the NYU School of Medicine and Langone Medical Center. Do not disclose or use except as authorized in writing by the study sponsor

- **Probably Related** – There is evidence to suggest a causal relationship, and the influence of other factors is unlikely. The clinical event, including an abnormal laboratory test result, occurs within a reasonable time after administration of the drug, is unlikely to be attributed to concurrent disease or other drugs or chemicals, and follows a clinically reasonable response on withdrawal (dechallenge). Rechallenge information is not required to fulfill this definition.
- **Possibly Related** – There is some evidence to suggest a causal relationship (e.g., the event occurred within a reasonable time after administration of the trial medication). However, other factors may have contributed to the event (e.g., the participant's clinical condition, other concomitant events). Although an AE may rate only as "possibly related" soon after discovery, it can be flagged as requiring more information and later be upgraded to "probably related" or "definitely related," as appropriate.
- **Unlikely to be related** – A clinical event, including an abnormal laboratory test result, whose temporal relationship to drug administration makes a causal relationship improbable (e.g., the event did not occur within a reasonable time after administration of the trial medication) and in which other drugs or chemicals or underlying disease provides plausible explanations (e.g., the participant's clinical condition, other concomitant treatments).
- **Not Related** – The AE is completely independent of study drug administration, and/or evidence exists that the event is definitely related to another etiology. There must be an alternative, definitive etiology documented by the clinician.

### 8.2.3 Expectedness

The principal investigator and/or Sub-investigator(s) will be responsible for determining whether an AE is expected or unexpected. An AE will be considered unexpected if the nature, severity, or frequency of the event is not consistent with the risk information previously described for the study regimen.

## 8.3 Time Period and Frequency for Event Assessment and Follow-Up

The occurrence of an AE or SAE may come to the attention of study personnel during study visits and interviews of a study participant presenting for medical care, or upon review by a study monitor. All AEs including local and systemic reactions not meeting the criteria for SAEs will be captured on the appropriate CRF. Information to be collected includes event description, time of onset, clinician's assessment of severity, relationship to study product (assessed only by those with the training and authority to make a diagnosis), and time of resolution/stabilization of the event. All AEs occurring while on study must be documented appropriately regardless of relationship. Treatment-related AEs will be followed to adequate resolution.

Any medical condition that is present at the time that the participant is screened will be considered as baseline and not reported as an AE. However, if the study participant's condition deteriorates at any time during the study, it will be recorded as an AE. UPs will be recorded in the data collection system throughout the study.

Changes in the severity of an AE will be documented to allow an assessment of the duration of the event at each level of severity to be performed. AEs characterized as intermittent, require documentation of onset and duration of each episode.

Adverse Events (AE) and Serious Adverse Events (SAE) are unexpected toxicities that occur in the transplant setting (i.e. hematologic, gastrointestinal toxicities are expected). The Common Terminology Criteria for Adverse Events, Version 5.0, will be used for assessing the severity of adverse events. The following will be reported and monitored:

- Grade 3 or higher, non-hematologic toxicity directly related to study drugs (such as peripheral neuropathy).
- Grade 2 or higher hepatic bilirubin.

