#### **2.4.3 Known Potential Benefits**

A potential benefit of linac based VMAT TBI, as opposed to our current approach of using opposed laterals to deliver TBI, is that we can minimize the dose to the lungs, without compromising coverage in the thoracic region outside of the lungs. This will have the potential of reducing the risk of idiopathic pneumonia syndrome while maximizing the effectiveness of TBI. We limit the mean dose to the kidneys, which has the potential to prevent renal dysfunction.

Since the initial writing of this protocol, Stanford has published their VMAT TBI experience which includes primarily pediatric patients (23/35 patients <18 years old). Their series includes 35 patients treated with VMAT TBI, 13 with doses of 12Gy or higher as per this protocol. Their dose objectives are similar to ours with a D90% $\geq$ 100% for the PTV body a Dmax $\leq$ 120%, Dmean of lungs  $\leq$ 660cGy. Of note, they also constrict their kidney dose and lens dose for myeloablative regimens. Their toxicity data (unpublished, data courtesy of [name] and [name]) is very favorable with a 4% rate of grade 2 pneumonitis (n=1, present before RT), 4% rate of grade 1 nephrotoxicity (n=1, present before RT), 40% diarrhea (4% grade 3), 56% rate of fatigue (all  $\leq$  grade 2), 76% rate of nausea (4% grade 3), 84% rate of mucositis (36% grade 3), and 16% rate skin toxicity (all  $\leq$  grade 1).

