#### CONFIDENTIAL

This material is the property of the NYU School of Medicine and Langone Medical Center. Do not disclose or use except as authorized in writing by the study sponsor

The PI will record all reportable events with start dates occurring any time after informed consent is obtained until at least 100 days (for non serious AEs) or up to one year post transplant (for SAEs) after the last day of study participation. . At each study visit, the investigator will inquire about the occurrence of AE/SAEs since the last visit. Events will be followed for outcome information until resolution or stabilization.

All unresolved adverse events should be followed by the investigator until the events are resolved, the subject is lost to follow-up, or the adverse event is otherwise explained. At the last scheduled visit, the investigator should instruct each subject to report any subsequent event(s) that the subject, or the subject's personal physician, believes might reasonably be related to participation in this study. The investigator should notify the study sponsor of any death or adverse event occurring at any time after a subject has discontinued or terminated study participation that may reasonably be related to this study. The sponsor should also be notified if the investigator should become aware of the development of cancer or of a congenital anomaly in a subsequently conceived offspring of a subject that has participated in this study.

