Serious adverse event reporting will begin in conjunction with the date of treatment administration. Any SAEs occurring prior to study drug administration that the investigator believes may have been caused by a protocol procedure must be reported immediately to the principal investigator, assigned medical monitor, with a notification email sent to [[contact]](mailto:[contact]) and recorded on the case report form.

All fatal or life-threatening adverse events must be immediately reported to the Principal Investigator, via appropriate reporting mechanism and the NYU Langone Health IRB by telephone or e-mail. Within 24 hours of the event, the Serious Adverse Event Form must be emailed to [[contact]](mailto:[contact]) whether full information regarding the event is known or not.

Additional follow-up by the investigator will be required if complete information is not known. De-identified source documentation of all examinations, diagnostic procedures, etc. which were completed with respect to the event should be included with the SAE form. For laboratory results, include the laboratory normal ranges.

All other serious adverse events must be reported to the principal investigator and DSMC's appointed medical monitor within 24 hours by e-mail ([[contact]](mailto:[contact])). The Serious Adverse Event Form must also be emailed to the principal investigator, assigned medical monitor and emailed to [[contact]](mailto:[contact]), this documentation will be forwarded to the appropriate additional personnel within 24 hours of the event whether full information regarding the event is known or not. Additional follow-up by the investigator will be required if complete information is not known.

Current contact information shall be maintained at the site within the regulatory binder.

All serious adverse events (SAEs) will be evaluated by the DSMC if meeting the requirements for

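### Section 8.3 defines adverse events as unexpected toxicities and ties its first monitoring item to study drugs, in conflict with sections 8.1.1, 8.1.2 and 8.2.3 and with a radiation intervention

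*Combined protocol and SAP*

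**What the plan says.** - Section 8.1.1: an AE "is any symptom, sign, illness or experience that develops or worsens in severity during the course of the study". Section 8.1.2 makes an AE serious by its outcome or medical importance. Neither definition mentions expectedness.
- Section 8.2.3: the principal investigator and sub-investigators "will be responsible for determining whether an AE is expected or unexpected".
- Section 8.3, first paragraph: "All AEs occurring while on study must be documented appropriately regardless of relationship". It also sends non-serious AEs to the CRF.
- Section 8.3, the later paragraph that introduces CTCAE version 5.0: "Adverse Events (AE) and Serious Adverse Events (SAE) are unexpected toxicities that occur in the transplant setting (i.e. hematologic, gastrointestinal toxicities are expected". Two items follow for reporting and monitoring: "Grade 3 or higher, non-hematologic toxicity directly related to study drugs (such as peripheral neuropathy", and bilirubin of grade 2 or higher.
- Section 8.3, continued on the next page: the PI records events that are reportable, with start dates "any time after informed consent is obtained".
- Section 8.4.2: "Serious adverse event reporting will begin in conjunction with the date of treatment administration". Earlier SAEs are reported if the investigator thinks a protocol procedure caused them.
- Section 6.1: the intervention is VMAT delivery with a 6 MV photon beam. No study drug is named.
- Section 10.1: analyses cover patient characteristics, dosimetry, IPS, the day-100 composite and EFS. No AE tabulation is specified.

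**The concern.** One term carries two definitions, and the recording rules depend on that term. Staff who follow 8.1.1 record an expected gastrointestinal or hematologic event as an AE. Staff who follow the later text of 8.3 may decide that it is not one. The monitoring item adds to the problem because it asks for a causal link to something the trial does not administer as its intervention.

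The stake is the acute toxicity record. Section 2.3 gives confirmation of safety as part of the rationale, and much of the acute toxicity that the protocol describes in sections 2.2.2 and 2.4.3 is mucositis, nausea and diarrhea. The schedule in section 7 requires at least one on-treatment visit. The next study visit comes more than 100 days after transplant. Events in between are found largely from records and interval history, so the definition that staff have in mind matters.

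**Working it through.** The core of this is a comparison of texts. The plan has no figure to reproduce.

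**1. One event under each definition.** Take an expected gastrointestinal toxicity of grade 3 that prolongs a hospital stay.

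| Text | Classification |
|---|---|
| 8.1.1 | AE |
| 8.1.2 | SAE, because the stay is prolonged |
| 8.2.3 | AE, labelled expected |
| 8.3, first paragraph | AE, documented whatever its relationship |
| 8.3, later paragraph | Not an AE or SAE, because it is not unexpected |

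The last row cannot be true together with the four above it.

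**2. The list for reporting and monitoring.** The first item requires a direct link to study drugs. A grade 3 non-hematologic toxicity caused by radiation fails that condition on a literal reading. The bilirubin item has no such condition. Section 8.4.1 separately lists IPS of grades 1 to 5. So, apart from IPS, nothing in these lists explicitly addresses radiation toxicity.

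**3. Does other text settle the conflict?**
- The recording rules in the first paragraph of 8.3 and in 8.4.1 apply to AEs, which is the term in dispute.
- The continuation of 8.3 speaks of reportable events, which can be read as pointing back to the short list.
- Section 14.1 has expected adverse reactions entered in the database, but names them beside AEs as if separate. That secures data entry. It does not say whether they count as AEs.
- Section 10.1 has no AE table, so the analysis plan does not decide what is counted.

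**4. Starting points.** Section 8.3 starts recording at consent. Section 8.4.2 starts SAE reporting at treatment, with the procedure-related exception. An SAE between consent and treatment that no protocol procedure caused is recorded under 8.3 but falls outside SAE reporting under 8.4.2.

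**5. Illustrative scale.** Section 2.4.3 cites an external VMAT series with "84% rate of mucositis (36% grade 3"), 76% nausea and 40% diarrhea. Applied to 35 subjects:
- mucositis: 35 × 0.84 = 29.4, about 29
- grade 3 mucositis: 35 × 0.36 = 12.6, about 13
- nausea: 35 × 0.76 = 26.6, about 27
- diarrhea: 35 × 0.40 = 14.0

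These are weak inputs. In that source one patient is 4%, so the toxicity denominator is about 1 / 0.04 = 25. The series is mainly pediatric (23 of 35 under 18), and only 13 of its 35 patients received 12 Gy or more. Section 2.2.2 shows how far rates vary. One linac VMAT series reports grade 3 mucositis in all seven patients, and another reports no acute radiation toxicity of grade 3 or more in thirty. On those two, grade 3 mucositis in 35 subjects would run from 35 × 0/30 = 0 to 35 × 7/7 = 35. Counting mucositis as gastrointestinal is an assumption; the protocol does not classify it.

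**The case against.** The strongest reply is that this is leftover template wording, outweighed by the rest of the protocol. The on-treatment visit (section 7.3.2) assesses acute side effects. Section 8.4.1 puts all adverse events in the source record and the CRF. Section 8.4.2 sends AEs that are not immediately reportable to the IRB at annual review, and section 12 includes a summary of all AEs in the annual IRB report. Section 14.1 names expected reactions as data to be entered. Section 8.6 takes every death and immediately life-threatening event irrespective of attribution. Section 9.1.1 puts cumulative toxicities, as well as AEs and SAEs, before the DSMC.

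Most of this stands, and it rules out several stronger readings that a reader might infer:
- **Expected radiation toxicities are removed from the safety data.** That follows only if one sentence overrides all the texts above. The sentence also names only hematologic and gastrointestinal toxicities, not skin or renal events.
- **The DSMC would not see these events.** Section 9.1.1 says otherwise.
- **Monitoring is limited to drug-related events.** Bilirubin, IPS, deaths and immediately life-threatening events carry no drug condition.
- **The trial would report a falsely low rate against the series in 2.4.3.** That series is background. No objective or endpoint compares mucositis, nausea, diarrhea or skin rates with it.
- **The start dates flatly contradict each other.** Recording and reporting are different acts, and the procedure-related exception narrows the gap.

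What the reply does not do is remove the conflict. It shows that wider capture is probably intended, while a stated definition still says the opposite and the first monitoring item still names the wrong kind of intervention.

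**Conclusion.** The contradiction holds. The later text of 8.3 cannot be reconciled with 8.1.1, 8.1.2, 8.2.3 or its own first paragraph, and its first monitoring item does not fit a radiation trial. The consequence is a risk of inconsistent recording, or of omission from AE and SAE counts, for expected gastrointestinal and hematologic events. Certain loss is not shown.

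The size of that risk cannot be computed from the documents, because it depends on which text staff follow. The counts from the external series show only that the event classes concerned may be common. The primary endpoint is dosimetric and is unaffected, and IPS has its own definition and grading. The point should be corrected because it bears on how any toxicity summary from this trial can be read.

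**What to change.** - In 8.3, delete the sentence that equates AEs and SAEs with unexpected toxicities, so that 8.1.1 and 8.1.2 govern.
- State that expectedness affects expedited reporting only and never whether an event is recorded.
- In the first item for reporting and monitoring, replace the reference to study drugs and its neuropathy example with the study intervention, VMAT TBI.
- Keep the present capture of all AEs and the one-year window for SAEs. Do not substitute a shorter list of organ systems or a cut-off at day 100; either would be narrower than what the protocol now requires.
- Reconcile the start of recording in 8.3 (consent) with the start of SAE reporting in 8.4.2 (treatment, apart from procedure-caused events), and say which rule governs which act.
- In 10.1, add a table of maximum CTCAE version 5.0 grade per subject.

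The cost is a wording amendment, slightly more AE abstraction by staff who already record AEs, and one descriptive table. No change to sample size, visits or treatment is involved.

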#### CONFIDENTIAL

This material is the property of the NYU School of Medicine and Langone Medical Center. Do not disclose or use except as authorized in writing by the study sponsor

The PI will record all reportable events with start dates occurring any time after informed consent is obtained until at least 100 days (for non serious AEs) or up to one year post transplant (for SAEs) after the last day of study participation. . At each study visit, the investigator will inquire about the occurrence of AE/SAEs since the last visit. Events will be followed for outcome information until resolution or stabilization.

All unresolved adverse events should be followed by the investigator until the events are resolved, the subject is lost to follow-up, or the adverse event is otherwise explained. At the last scheduled visit, the investigator should instruct each subject to report any subsequent event(s) that the subject, or the subject's personal physician, believes might reasonably be related to participation in this study. The investigator should notify the study sponsor of any death or adverse event occurring at any time after a subject has discontinued or terminated study participation that may reasonably be related to this study. The sponsor should also be notified if the investigator should become aware of the development of cancer or of a congenital anomaly in a subsequently conceived offspring of a subject that has participated in this study.

